Biochemistry-A ^b	-14	-	-	-	-	-	-	X	-	-	-	X	X	X	-	-	-	X	X	X	-	
Biochemistry-B ^b	-14	-	-	-	-	-	-	X	-	-	-	-	-	X	-	-	-	-	X	X	-	
Calculated CLcr (Cockcroft and Gault's formula) ^{b, d}	-14	-	-	-	-	-	-	X	-	-	-	X	X	X	-	-	-	X	X	X	-	
Detection of SARS-CoV-2 (COVID-19) by PCR	-14	-	-	-	-	-	-	-	-	-	-	-	-	-	-	-	-	-	-	-	-	
Pregnancy test (serum β-hCG) (only if the patient is a WOCBP)	-14	-	-	-	-	-	-	X	-	-	-	-	-	X	-	-	-	-	X	X	-	
ECG ^e	-14	-	-	-	-	-	-	X	-	-	-	-	-	X	-	-	-	-	-	X	-	
LVEF (by ECHO or MUGA) ^f	-14	-	-	-	-	-	-	-	-	-	-	-	-	-	-	-	-	-	-	X	-	
Randomization ^g	-14	-	-	-	-	-	-	-	-	-	-	-	-	-	-	-	-	-	-	-	-	
Bosentan delivery and patient's diary ^h	-	X	-	-	-	-	-	-	-	-	-	-	-	-	-	-	-	-	-	-	-	
Prophylactic medication ⁱ	-	-	-	-	-	-	-	X	-	-	-	-	-	X	-	-	-	-	X	-	-	
Lurbinectedin 1h (-5/+20 min) infusion	-	-	-	-	-	-	-	X	-	-	-	-	-	X	-	-	-	-	X	-	-	
Bosentan oral administration	-	-	X	X	X	X	X	X ^j	-	-	-	-	-	-	-	-	-	-	-	-	-	
Contact to patients (via telephone or other) ^k	-	-	X	X	X	X	X	-	-	-	-	-	-	-	-	-	-	-	-	-	-	
AAG blood sample collection	-	-	-	-	-	-	-	X	-	-	-	-	-	X	-	-	-	-	-	-	-	
IL6 blood sample collection	-	-	-	-	-	-	-	X	-	-	-	-	-	X	-	-	-	-	-	-	-	

Study Period►	Screening (days prior to registration)	Cycle 1												Cycle 2						Cycle 3	End of Treatment	Follow-up AEs
		-6	-5	-4	-3	-2	-1	1*	2	3	5	8	15	1	2	3	5	8	15			
Cycle Day►																						
PGt blood sample collection (only if written IC given) ¹	-	-	-	-	-	-	-	One blood sample collected at any time during the study, but preferably just before lubrinezdin treatment start in Cycle 1												-	-	
Lurbinectedin PK blood sample collection ^m	-	-	-	-	-	-	-	X	X	X	X	X	-	X	X	X	X	X	-	-	-	-
Bosentan PK blood sample collection ^m	-	-	-	-	-	-	-	X	X	-	-	-	-	-	-	-	-	-	-	-	-	-
AEs ⁿ	Continuous ^o																		X ^p			
Intercurrent events, concomitant disease and therapies	Continuous																		-			

Registration = confirmation of eligibility and inclusion; Day 1 = the day of lubrinezdin administration (with infusion start) of cycle 1 or 2; Day 8 = seven days after the lubrinezdin administration of cycle 1 or 2 (± 2 days); Day 15 = fourteen days after the lubrinezdin administration of cycle 1 or 2 (± 2 days).

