*** Permitted windows for assessments before Day 1 of Cycle 1:**

If physical examination, ECOG PS, vital signs, Hematology, Biochemistry-A, Biochemistry-B, CLcr (provided only if serum creatinine levels are above ULN) and Coagulation were assessed >10 days before Day 1 of Cycle 1, the tests must be repeated the day before or the Day 1 (always prior to lubrinezdin infusion).

If pregnancy test was done >7 days before Day 1 of Cycle 1, the test must be repeated the day before or the Day 1 (always prior to lubrinezdin infusion).

A patient should only be treated if eligibility criteria are still met according to assessments performed closest to treatment start.

Permitted windows for assessments after Day 1 of Cycle 1:

A ± 2 -day time window will be allowed for Hematology, Biochemistry-A and CLcr (provided only if serum creatinine levels are above ULN) on Day 8 and Day 15, and for vital signs on Day 8 of Cycle 1.

A -1 day window will be allowed for physical examination, ECOG PS, vital signs, Hematology, Biochemistry-A, and Biochemistry-B, CLcr (provided only if serum creatinine levels are above ULN) and Pregnancy test on Day 1 of Cycle 2 and further cycles (always prior to lubrinezdin infusion).

A $+2$ days window for Day 1 lubrinezdin administration of Cycle 3.

If a drug administration is delayed beyond the permitted protocol window, assessments planned for the original administration day must be repeated on the day the dose is finally administered.

^a Should treatment be administered more than ten days after the screening tests, repeat these tests prior to the first infusion and if clinically indicated. Height needs to be measured at baseline only. BSA will not be reported at the EOT. BSA calculated according to DuBois formula (see [Appendix 4](#)).

^b Any patient having any grade ≥ 3 laboratory abnormalities and/or treatment-related AEs is suggested to have the relevant tests re-assessed at intervals of at least 72 hours but not more than one week until recovery to at least grade 2 has been documented.

^c Repeat during treatment period and at EOT if clinically indicated.

^d Calculated CLcr [Cockcroft and Gault's formula] should be provided only if serum creatinine levels are above ULN.

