5.2 PLANNED STUDY PERIODS (INDIVIDUALLY PER PATIENT)

Patients will be evaluated at scheduled visits in three study periods:

- **Pre-treatment (screening)**: from signature of the ICF to the day of first administration of the study treatment (bosentan or lorbinectedin).
- **Treatment**: from first administration of the study treatment (bosentan or lorbinectedin) to the last dose of lorbinectedin plus 31 days (end-of-treatment, EOT) (maximum of three cycles).
- **Follow-up of adverse events**: after EOT, patients with treatment-related toxicities $>$ grade 2 will be followed every four weeks until recovery to at least grade 1 or stabilization of all treatment-emergent AEs, or until the start of a new antitumor therapy, until the continuation of treatment outside this study under a Compassionate Use Agreement or death, whichever occurs first.

Patients will be considered to be **on-study** from the signature of the ICF to the end of the follow-up period. Patients will be considered to be **on-treatment** for the duration of their treatment and until the day of EOT, immediately before the start of the follow-up period.

An end-of-treatment visit will be performed within 31 days (± 10 days) after administration of the last dose of lorbinectedin, unless the patient dies or starts any new antitumor therapy outside this clinical study, in which case the EOT visit should be performed immediately before the start of the new therapy (ideally the day before or the same day).

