4. Detection of SARS-CoV-2 (COVID-19)	
 ♦ PCR for SARS-CoV-2 (COVID-19) in nasopharyngeal/oropharyngeal swabs and nasal swabs. 	Sequence 1 (TR) and Sequence 2 (RT): Within 14 days prior to day of registration. ^a
5. Pregnancy test	Assessment of β-hCG (serum) only if the patient is a WOCBP (Appendix 2).	Sequence 1 (TR) and Sequence 2 (RT): Within 14 days prior to day of registration. ^a
6. Cardiac assessment	
 ♦ ECG: Cardiac rhythm will be done in triplicate and identified in ECG intervals of at least 30 seconds of duration, PR interval, QT interval (raw and corrected by HR using Bazett's formula) ♦ LVEF: ECHO or MUGA scan. 	Sequence 1 (TR) and Sequence 2 (RT): Within 14 days prior to day of registration. ^a Sequence 1 (TR) and Sequence 2 (RT): A previous LVEF assessment could be used if was made within 28 days prior to screening, if no previous assessment available; perform within 14 days prior to day of registration. ^a
7. Bosentan delivery and patient's diary	-	Only in Sequence 1 (TR): Day -6 with a -2/+1 day time window (i.e., from Day -8 to Day -5), but after the registration.

	ASSESSMENT	TIME
8. Intercurrent events, concomitant disease and therapies	-	Sequence 1 (TR) and Sequence 2 (RT): Within 14 days prior to day of registration. ^a
9. Adverse events	Clinical assessment of the patient's signs and symptoms. ^c Only information on SAEs that occurred after signature of the informed consent is required before treatment start. Grading should be as per the NCI-CTCAE v.5.	Sequence 1 (TR) and Sequence 2 (RT): Within 14 days prior to day of registration. ^a

Permitted windows for assessments before Day 1 of Cycle 1:

If physical examination, ECOG PS, vital signs, Hematology, Biochemistry-A, Biochemistry-B, CLcr (provided only if serum creatinine levels are above ULN) and Coagulation were assessed >10 days before Day 1 of Cycle 1, the tests must be repeated the day before or the Day 1 (always prior to lurbinectedin infusion).

If pregnancy test was done >7 days before Day 1 of Cycle 1, the test must be repeated the day before or the Day 1 (always prior to lurbinectedin infusion).

A patient should only be treated if eligibility criteria are still met according to assessments performed closest to treatment start.

^a Sequence 1 (TR)/ Sequence 2 (RT): day of registration, confirmation of eligibility.

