6.2 PATIENT REGISTRATION

Eligibility will be checked before registration confirmed by the Sponsor. The patient will be a screening failure if not all inclusion criteria are met, if any exclusion criterion is met, or if the Sponsor does not approve registration. Regardless of circumstances, Investigators will not be allowed to treat any patient before appropriate receipt of the Sponsor's agreement to proceed with registration. A patient should only be treated if eligibility criteria are still met according to assessments performed closest to first drug administration.

A patient who has been treated without the Sponsor's agreement may not be considered evaluable for the primary endpoint of the study and may need to be replaced (although can continue in treatment provided this does not pose a risk to the patient until discontinuation for any other reason).

For patients included in the study (all registered patients) but never treated, only the applicable forms at baseline and off-study visit modules of the eCRF should be completed but serious adverse events (SAEs) occurring during screening period need to be reported (using paper SAE forms).

For screen failures (patients who started screening but were not finally registered), only the screening form of the eCRF should be completed but SAEs occurring during screening need to be reported (using paper SAE forms).

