	
 ♦ Coagulation (INR): 	
Sequence 1 (TR) and Sequence 2 (RT): Repeat on Day 1 of Cycle 1 (prior to lorbinecetin infusion) if more than ten days have passed since the screening assessment. Also repeat if clinically indicated.

	
 ♦ Calculated CLcr: Cockcroft and Gault's formula (Appendix 4).^c 	
Sequence 1 (TR) and Sequence 2 (RT): Cycle 1: Day 8 and Day 15. Also repeat on Day 1 of Cycle 1 (prior to lorbinecetin infusion) if more than ten days have passed since the screening assessment. Cycle 2: Day 1, Day 8 and Day 15. Cycle 3: Day 1. (always prior to lorbinecetin infusion).

3. Pregnancy test	Only applicable to WOCBP. Assessment of β-hCG (in serum).	During the on-treatment period, testing should be done be every cycle (always prior to lorbinecetin infusion). Also repeat on Day 1 of Cycle 1 (prior to lorbinecetin infusion) if more than seven days have passed since the screening assessment.
4. Pharmacokinetics	
 ♦ Cycle 1 and Cycle 2: Eleven blood samples each (before lorbinecetin infusion start, 5 min before end of lorbinecetin infusion and 30 min, 1 hour, 2 hours, 4 hours, 6 hours, 24 hours, 48 hours, 96 hours, 168 hours after the end of lorbinecetin infusion) will be collected for pharmacokinetic analyses (see details in Section 8.1.1). 	
Sequence 1 (TR) and Sequence 2 (RT): Cycle 1 and Cycle 2. PK sampling for bosentan will be done in Cycle 1 for patients assigned to Sequence 1 (TR), and in Cycle 2 for assigned to Sequence 2 (RT). See Table 9.

5. AAG and IL6 collection	One blood sample per cycle.	Sequence 1 (TR) and Sequence 2 (RT): On Day 1 of Cycle 1 and Cycle 2 (always prior to lorbinecetin infusion).
6. Pharmacogenetics (only if written informed consent given)	One blood sample.	Sequence 1 (TR) and Sequence 2 (RT): At any time during the study, but preferably just before lorbinecetin infusion start in Cycle 1.
7. ECG	ECG should be done in triplicate and cardiac rhythm will be identified in ECG intervals of at least 30 seconds of duration, PR interval, QT interval (raw and corrected by HR using Bazett's formula).	Sequence 1 (TR) and Sequence 2 (RT): On Day 1 of Cycle 1 and Cycle 2, 5 minutes before SOI (-25 to -1 min before preinfusion PK samples collection) and 1 hour after EOI (-15 to -1 min before the PK sample collection).

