7.2 ADMINISTRATION OF THE STUDY MEDICATION

Bosentan

Bosentan will be administered orally twice daily as 125 mg film-coated tablets.

In the co-administration cycles, bosentan will be administered orally twice daily in the morning and in the evening from Day -5 to Day -1 (i.e., five days before lurbinectedin infusion), and once daily on Day 1 (i.e., the day of lurbinectedin infusion), following recommendations at the Summary of Product Characteristics (SmPC). On Day 1 (i.e., day of lurbinectedin infusion), bosentan will be given immediately prior to the start of the lurbinectedin infusion. In fact, bosentan should be administered after obtaining the bosentan PK sample #1 and before the start of lurbinectedin infusion (-15 min to -1 min). In case of lurbinectedin delay (≤ 2 days), bosentan could be administered twice daily during a maximum of seven consecutive days before lurbinectedin infusion, and supplied at the study center once daily on Day 1 (before lurbinectedin infusion).

In Sequence 1 (TR), bosentan for self-administration and the patient’s diary should be given to the patient on Day -6 with a -2/+1 day time window (i.e., from Day -8 to Day -5). In Sequence 2 (RT), bosentan and the patient’s diary should be given to the patient on Day -6 of Cycle 2 with a -2/+1 day time window (i.e., from Day 14 of Cycle 1 to Day -5 of Cycle 2).

In addition, the study center will contact the patients (via telephone or other methods) daily during bosentan intake to remind them or confirm that they have taken the morning and evening dose of bosentan when they are not at the study center.

Lurbinectedin

Lurbinectedin will be administered as a 1-hour (-5/+20 min) i.v. infusion on Day 1 q3wk, over a minimum of 100 mL dilution on 5% glucose or 0.9% sodium chloride via a central line (or a minimum of 250 mL dilution if a peripheral line is used).

Patients will receive a maximum of three cycles: two consecutive cycles of lurbinectedin, one cycle with and one cycle without bosentan co-administration (in different order depending on the Sequence 1 or Sequence 2 of treatment), followed by a third cycle with lurbinectedin alone (this last cycle optional for patients with clinical benefit).

The dose of lurbinectedin when given in combination with bosentan will be 3.2 mg/m². Lurbinectedin dose will be based on the acceptability of the PK and safety results from the first three patients.

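### In Sequence 1 the 7-day pregnancy re-test limit counts back from the lurbinectedin infusion, so bosentan can start on a test 14 days old and the repeat comes only after 8 to 10 tablets

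*Protocol*

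**What the plan says.** **Re-test rule.** The notes to the Sequence 1 schedule state: "If pregnancy test was done >7 days before Day 1 of Cycle 1, the test must be repeated the day before", or on Day 1, in either case before lurbinectedin. The same note stands under Tables 4 and 5. The pregnancy row of Table 5 (section 6.4) asks for the repeat on Day 1 of Cycle 1 "if more than seven days have passed since the screening assessment". The schedule notes define Day 1 as the day of the lurbinectedin infusion.

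**Planned tests.** The Sequence 1 schedule row "Pregnancy test (serum β-hCG) (only if the patient is a WOCBP") is marked at screening and on Day 1 of Cycle 1, with nothing from Day -6 to Day -1. Table 4 (section 6.1) allows the screening test up to 14 days before registration.

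**Start of treatment.** Section 5.2 runs the treatment period "from first administration of the study treatment" and names bosentan or lurbinectedin as that treatment. Section 7.2 gives bosentan "twice daily in the morning and in the evening from Day -5 to Day -1". Table 4 places its delivery in Sequence 1 on "Day -6 with a -2/+1 day time window (i.e., from Day -8 to Day -5), but after the registration".

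**General safeguard.** Section 6.2 allows treatment only if eligibility still holds on the "assessments performed closest to first drug administration".

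**SAP.** Section 2 describes screening as falling within 14 days before the first dose of either drug, whereas the protocol counts from registration.

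**The concern.** In Sequence 1 the only limit on the age of the pregnancy test is tied to the second drug given. Bosentan comes five days earlier, and no test is scheduled between screening and the end of the home dosing period.

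Pregnancy is an exclusion (section 4.2, criterion 6), and inclusion criterion 9 in section 4.1 mentions teratogenic effects in animals in connection with bosentan. A pregnancy first found on Day -1 or Day 1 would already be a bosentan exposure, reportable within 24 hours under section 8.5.3. If lurbinectedin were then withheld, the woman would fall outside the safety population (section 9.1) and would have to be replaced (section 5.3).

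The schedule suggests an oversight. Before treatment starts, only serious adverse events need reporting. Note n of the two schedules ends that period at Day -5 in Sequence 1 and at Day -1 in Sequence 2, so the earlier start in Sequence 1 was recognised there. The pregnancy note reads the same in both sequences.

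**Working it through.** **Convention.** There is no Day 0: section 3.2 equates Day -5 with five days before the infusion, so Day -k is k days before Day 1. As a check, the delivery window of Day -6 with -2/+1 days gives -6 - 2 = -8 and -6 + 1 = -5, which matches Table 4.

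**Inputs.** Screening test up to 14 days before registration (Table 4); first tablet on Day -5, one 125 mg tablet twice daily to Day -1 (section 7.2); repeat on Day -1 or Day 1 if the test was more than 7 days before Day 1 (schedule notes).

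**Age of the oldest permitted test at the first tablet.** With registration on Day -r, the oldest test is on Day -(r + 14). Its age on Day -5 is (r + 14) - 5 = r + 9 days. There are 15 permitted test days. A test is more than 7 days old at the first tablet if done on Day -13 or earlier, which is (r + 14) - 12 = r + 2 of those days.

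| Registration | Oldest test | Age at first tablet | Test days giving an age over 7 days |
|---|---|---|---|
| Day -5 | Day -19 | 14 days | 7 of 15 |
| Day -6 | Day -20 | 15 days | 8 of 15 |
| Day -7 | Day -21 | 16 days | 9 of 15 |
| Day -8 | Day -22 | 17 days | 10 of 15 |

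The protocol states no maximum gap between registration and first dose. Registration on Day -10 would allow 19 days and on Day -14 would allow 23.

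**Under the SAP description.** If screening must fall within 14 days before the first tablet, the oldest test is on Day -19 and is 14 days old. Tests on Day -19 to Day -13 (7 days) would still be more than 7 days old.

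**Tests not counted.** Tests on Day -12 to Day -8 also trigger the current repeat, but they are only 3 to 7 days old at the first tablet.

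**Tablets before the repeat, no delay.**
- Day -1 before the morning dose: 4 × 2 = 8 tablets, 8 × 125 = 1000 mg.
- Day -1 after the evening dose, or Day 1 before that day's tablet: 5 × 2 = 10 tablets, 10 × 125 = 1250 mg.
- Day 1 after the tablet but before the infusion: 11 tablets.

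If lurbinectedin slips by the permitted two days and the repeat is timed to the actual infusion, the first two figures become 6 × 2 = 12 and 7 × 2 = 14 tablets.

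**With the limit tied to the first tablet.** The test is at most 7 days old at that point, and no tablets precede a required repeat. A test at the dispensing visit (Day -8 to Day -5) is 3 to 0 days old at the first tablet. It precedes the Day -1 or Day 1 test by 4 days (Day -5 to Day -1) to 8 days (Day -8 to Day 1).

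**The case against.** The strongest reply is that a check already exists. Pregnancy excludes a woman, eligibility is confirmed before registration, and bosentan is handed over only after that. Section 6.2 ties continued eligibility to the first drug, which in Sequence 1 is bosentan. A reader might infer that women could start bosentan untested, and the documents do not support that. What stands is narrower: section 6.2 relies on the latest assessment available, sets no maximum age and requires no new test. A negative result 14 days old satisfies it.

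Bosentan is also given "following recommendations at the Summary of Product Characteristics (SmPC"). That text is not available here, so any check it requires before treatment is unknown. The gap in the protocol's wording is certain; how often a woman would actually start on an old test is not.

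The 7-day limit was set for lurbinectedin, and no passage says that an older test is inadequate for bosentan. Applying it to bosentan is a proposal of this review. The protocol does, however, require contraception and a negative screening test and still asks for a fresh test after 7 days before the infusion.

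Three further inferences go too far. Ages of 15 to 17 days or more are not settled, because the SAP wording would cap the age at 14. The same gap cannot be claimed for Sequence 2: there lurbinectedin is the first drug in Cycle 1, and the pregnancy row of that schedule is missing from the text available. Nothing here biases the pharmacokinetic comparison.

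**Conclusion.** The point holds as a minor patient-safety fix. As written, the protocol lets a Sequence 1 patient start bosentan on a pregnancy test 14 days old: 14 to 17 days or more on the protocol's wording, at most 14 on the SAP's. The required repeat then follows 8 to 10 tablets if there is no delay. The 17-day figure assumes registration on Day -8, the earliest delivery day.

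The residual risk is small. A negative serum test at screening is required, as is highly effective contraception that is not solely hormonal during bosentan. Only women of childbearing potential among about four patients (8 randomised 1:1), plus replacements, are concerned. The sample size and the primary analysis are unaffected.

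**What to change.** For women of childbearing potential in Sequence 1, require a negative serum pregnancy test within 7 days before the first bosentan tablet. If the screening test is older, repeat it at the existing dispensing visit (Day -8 to Day -5) and hold the first tablet until the result is negative. Add this to the Sequence 1 schedule row and its notes, and to Tables 4 and 5.

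The pre-infusion rule needs a matching edit. The notes to the schedule and under Tables 4 and 5 count from whichever test was done, so a dispensing-visit test on Day -7 to Day -5 would satisfy them and cancel the Day -1 or Day 1 repeat. The pregnancy row of Table 5 already counts from the screening test. Reword the notes to match it, so that the new test adds to the pre-infusion test and does not replace it.

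The cost is protocol wording, one conditional mark in the schedule and at most one extra serum test per affected woman, with no extra visit. A site without same-day results must dispense before Day -5 or hold the first tablet for a short time.

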*** Permitted windows for assessments before Day 1 of Cycle 1:**

If physical examination, ECOG PS, vital signs, Hematology, Biochemistry-A, Biochemistry-B, CLcr (provided only if serum creatinine levels are above ULN) and Coagulation were assessed >10 days before Day 1 of Cycle 1, the tests must be repeated the day before or the Day 1 (always prior to lurbinectedin infusion).

If pregnancy test was done >7 days before Day 1 of Cycle 1, the test must be repeated the day before or the Day 1 (always prior to lurbinectedin infusion).

A patient should only be treated if eligibility criteria are still met according to assessments performed closest to treatment start.

Permitted windows for assessments after Day 1 of Cycle 1:

A ± 2-day time window will be allowed for Hematology, Biochemistry-A and CLcr (provided only if serum creatinine levels are above ULN) on Day 8 and Day 15, and for vital signs on Day 8 of Cycle 1.

A -1 day window will be allowed for physical examination, ECOG PS, vital signs, Hematology, Biochemistry-A, and Biochemistry-B, CLcr (provided only if serum creatinine levels are above ULN) and Pregnancy test on Day 1 of Cycle 2 and further cycles (always prior to lurbinectedin infusion).

A + 2 days window for Day 1 lurbinectedin administration of Cycle 3.

If a drug administration is delayed beyond the permitted protocol window, assessments planned for the original administration day must be repeated on the day the dose is finally administered.

^a Should treatment be administered more than ten days after the screening tests, repeat these tests prior to the first infusion and if clinically indicated. Height needs to be measured at baseline only. BSA will not be reported at the EOT. BSA calculated according to DuBois formula (see [Appendix 4](#)).

^b In case of detected abnormalities on Day 15 in sequence RT, these assessments should be repeated every 48-72 hours until recovery to retreatment criteria. Initiation of cycle 2 will be delayed accordingly in order to ensure that pre-treatment with bosentan is fulfilled.

^c Repeat during treatment period and at EOT if clinically indicated.

^d Calculated CLcr [Cockcroft and Gault's formula] should be provided only if serum creatinine levels are above ULN.

^e ECG should be done in triplicate (at screening, Day 1 and EOT visit) and allow rhythm definition (at least 30 seconds of duration), PR interval and QT interval (raw and corrected by HR using Bazett's formula). On Day 1, 5 minutes before SOI (-25 to -1 min before preinfusion PK samples collection) and 1 hour after EOI (-15 to -1 min before the PK sample collection), both will be done in triplicate.

^f A previous LVEF assessment could be used if was made within 28 days prior to screening and will be repeated if clinically indicated, and EOT.

^g Randomization apply for all patients.

^h Bosentan for self-administration and the patient's diary should be given to the patient on Day 15 of Cycle 1 standing for Day -6 of Cycle 2 with a -2/+1 day time window (i.e., from Day 14 of Cycle 1 to Day -5 of Cycle 2) in absence of delays.

ⁱ Corticosteroids i.v. (according to institutional standard antiemetic doses, minimum dose of 8 mg/day and maximum dose of 20 mg/day of dexamethasone sodium phosphate or equivalent); If feasible, anti-emetic medication and dose administered in Cycle 1 should be maintained in Cycle 2. Serotonin (5-HT₃) antagonists (ondansetron at least 8 mg i.v. and no more than 16 mg of ondansetron) (i.e., 30 ± 5 minutes before lurbinectedin administration).

^j If patient does not fulfill re-treatment criteria (Cycle 2 in RT sequence) in Day 1 assessments and lurbinectedin administration is postponed no more than two days, bosentan should not be

Study Period►	Screening (days prior to registration)	Cycle 1						Cycle 2									Cycle 3		End of Treatment	Follow-up AEs	
		1*	2	3	5	8	15	-5	-4	-3	-2	-1	1	2	3	5	8	15	1	31 (±10)	
Cycle Day►																					

discontinued.

^k The study center will contact the patients (via telephone or other methods) to remind them or confirm that they have taken the morning and evening dose of bosentan when they are not at the study center.

^l Blood sample for genotyping will be collected at any time during the study but preferably just before infusion start in Cycle 1, only if written IC for the pharmacogenetic sub-study is given.

^m Serial peripheral venous blood samples for determination of lirbunectedin (total and unbound), lirbunectedin metabolites (i.e., M1 and M4) and bosentan plasma concentrations will be collected at the time points indicated in Section 8.1.1, Table 9.

ⁿ Clinical assessment of the patient's signs and symptoms (including nurses' assessment and patient-reported issues) should continue on an ongoing basis throughout the study and be reported at least every cycle as AEs. Only information on SAEs that occurred after signature of the informed consent and up to Day -1 is required before treatment start. Grading should be as per the NCI-CTCAE v.5. Signs and symptoms will be assessed by the Sponsor as all the events ongoing during the screening period, except for prior history conditions, which should be reported in the medical history form. Ongoing events during the screening period are those present at any time between the informed consent date and the first drug administration, regardless of if they may be resolved or not at the date of Cycle 1 Day 1.

^o The "AE form" will be used only for events that occur after the first drug infusion or any event related to a study procedure within the study period (according to ICH guidelines); and to report 'ongoing' baseline conditions in case of any significant change (improvement or worsening) during the study.

^p Patients will be followed every four weeks until recovery to at least grade 1 or stabilization of all treatment-emergent AEs, or until the start of a new antitumor therapy, until the continuation of treatment outside this study under a Compassionate Use Agreement or death, whichever occurs first.

Hematology: Differential WBC (including neutrophils, monocytes and lymphocytes), erythrocytes, hemoglobin, hematocrit and platelets.

Coagulation: INR

Biochemistry A: AST, ALT, AP, lactate dehydrogenase (LDH), creatinine, glucose, creatine phosphokinase (CPK), CPK-MB fraction (if CPK is elevated above the normal range) and gamma glutamyltransferase (GGT) and total bilirubin (direct bilirubin if total bilirubin is above the ULN).

Biochemistry B: Serum electrolytes (Na⁺, K⁺, Mg⁺⁺), total calcium, total proteins, albumin, C-reactive protein (CRP).

AAG, alpha-1 acid glycoprotein; AE, adverse events; ALT, alanine aminotransferase; AP, alkaline phosphatase; AST, aspartate aminotransferase; β-hCG, beta subunit of human chorionic gonadotropin; BP, blood pressure; BSA, body surface area; CLcr, Creatinine clearance; CPK, creatine phosphokinase; CPK-MB, creatine phosphokinase-isoenzyme MB; CRP, C-reactive protein; D, day; ECG, electrocardiogram; ECHO, echocardiogram; ECOG PS, Eastern Cooperative Oncology Group Performance Status; EOT, end of treatment; GGT, gamma glutamyltransferase; HR, heart rate; IC, informed consent; ICF, informed consent form; ICH, International Conference on Harmonization; IL6, interleukin 6; INR, International Normalized Ratio; LDH, lactate dehydrogenase; LVEF, left ventricular ejection fraction; min, minutes; MUGA, multiple-gated acquisition scan; NCI-CTCAE, National Cancer Institute Common Toxicity Criteria; PCR, polymerase chain reaction; PGt; Pharmacogenetic; PK, pharmacokinetics; RT, reference-test sequence; SAE, serious adverse event; SARS-CoV-2, severe acute respiratory syndrome coronavirus 2; SOI, start of infusion; T^a, temperature; ULN, upper limit of normal; WBC, white blood cells; WOCBP, women of childbearing potential.

LIST OF ABBREVIATIONS AND DEFINITION OF TERMS

AAG	Alpha 1-acid Glycoprotein
AE(s)	Adverse Event(s)
ADR	Adverse Drug Reaction
ALT	Alanine Aminotransferase
ANC	Absolute Neutrophil Count
AP	Alkaline Phosphatase
ASCO	American Society of Clinical Oncology
AST	Aspartate Aminotransferase
AUC	Area Under the Concentration-time Curve
AUC_{last}	Area Under the Concentration-time Curve up to the last Measurable Concentration
AUCR	Area Under the Concentration-time Curve Ratio
β-hCG	Beta Subunit of Human Chorionic Gonadotropin
BEV	Bevacizumab
BM	Bone Marrow
BOS	Bosentan
BP	Blood Pressure
BSA	Body Surface Area
¹⁴C	Radioactive Carbon
CI	Confidence Interval
CL	Clearance
CLcr	Creatinine Clearance
C_{max}	Maximum Plasma Concentration
CNS	Central Nervous System
COPD	Chronic Obstructive Pulmonary Disease
CPK	Creatine Phosphokinase
CPK-MB	Creatine Phosphokinase Isoenzyme MB
CRO	Contract Research Organization
CUP	Carcinoma of Unknown Primary Site
CV	Coefficient of Variation
CYP	Cytochrome P450
D	Day
DDI	Drug-drug Interaction
DOX	Doxorubicin
DP	Drug Product
DSBs	Double-strand Breaks
ECG	Electrocardiogram
ECHO	Echocardiogram
ECOG PS	Eastern Cooperative Oncology Group Performance Status
eCRF	Electronic Case Report Form
EFTs	Ewing's Family of Tumors
EMA	European Medicines Agency
EOI	End of Infusion
EOT	End-of-treatment
EPO	Erythropoietin
FD	Flat Dose
FDA	Food and Drug Administration
FiH	First-in-Human
GCP	Good Clinical Practice
G-CSF	Granulocyte Colony Stimulating Factor
GCT	Germ Cell Tumor
GDPR	General Data Protection Regulation
GEM	Gemcitabine
GGT	Gamma-glutamyltransferase
GI	Gastrointestinal
GLP	Good Laboratory Practice
GM-CSF	Granulocyte Macrophage Colony Stimulating Factor
GMT	Greenwich Mean Time
h	Hour(s)

Hb	Hemoglobin
HL	Half-life
HR	Heart Rate; Homologous Recombination
HRD	Homologous Recombination-deficient
5-HT₃	Serotonin
IB	Investigator's Brochure
IC	Informed Consent
IC₅₀	Half Maximal Inhibitory Concentration
ICF	Informed Consent Form
ICH	International Conference on Harmonization
IEC	Independent Ethics Committee
IL-6	Interleukin 6
IMP	Investigational Medicinal Product
INR	International Normalized Ratio
IUD	Intra-uterine Contraceptive Device
i.v.	Intravenous
L	Liter
LC-MS/MS	Liquid Chromatography with Tandem Mass Spectrometry
LDH	Lactate Dehydrogenase
LMWH	Low Molecular Weight Heparin
LRB	Lurbinectedin
LVEF	Left Ventricular Ejection Fraction
MBC	Metastatic Breast Cancer
Min	Minutes
Mg	Milligram
mL	Milliliter
MRT	Mean Residence Time
MUGA	Multiple-gated Acquisition Scan
NA	Not Applicable
NCI-CTCAE	National Cancer Institute Common Toxicity Criteria
NER	Nucleotide Excision Repair
NET	Neuroendocrine Tumor
NHEJ	Non-homologous End Joining
NHP	Non-human Primates
NIHS	National Institute of Health Sciences
NSCLC	Non-small cell Lung Cancer
ORR	Overall Response Rate
OS	Overall Survival
OS6	Overall Survival Rate at Six Months
PBPK	Physiologically Based Pharmacokinetic Models
PCR	Polymerase Chain Reaction
PD	Progressive Disease
PFS	Progression-free Survival
PGt	Pharmacogenetic
PK	Pharmacokinetics
PKPD	Pharmacokinetics and Pharmacodynamics
PLD	Pegylated Liposomal Doxorubicin
PN	Peripheral Neuropathy
PRBC	Packed Red Blood Cells
PS	Performance Status
PVC	Polyvinyl Chloride
q3wk	Every Three Weeks
qd	Daily
R	Randomized
RD	Recommended Dose
RECIST	Response Evaluation Criteria in Solid Tumors
RSI	Reference Safety Information
RT	Reference-Test Sequence
SAE(s)	Serious Adverse Event(s)

SARS-CoV-2	Severe Acute Respiratory Syndrome Coronavirus 2
SCLC	Small Cell Lung Cancer
SD	Stable Disease
SDev	Standard Deviation
SmPC	Summary of Product Characteristics
SOI	Start of Infusion
SUSAR	Suspected Unexpected Serious Adverse Reaction
T^a	Temperature
T_{1/2}	Terminal Half-life
TAM	Tumor-associated Macrophage
T_{max}	Time at Which the Maximum Plasma Concentration is Observed
TR	Test-Reference Sequence
UK	Unknown
ULN	Upper Limit of Normal
Vs.	Versus
V_{ss}	Volume of Distribution at Steady State
V_z	Volume of Distribution on the Terminal Phase
WBC	White Blood Cells
wk	Week(s)
WOCBP	Woman of Childbearing Potential.

